#### 4.3 STUDY ENDPOINTS

#### 4.3.1 OUTCOME MEASURES

- 1. Independent Photographic Review of before and after images compared to baseline at D90 and baseline compared to D180.
- 2. Bilateral analysis of change to Morphometric breast measurements as per Brown, An Analysis of Ptosis at baseline and at day 30, 90, and 180 post-treatment.
- Bilateral analysis of change to Ptosis Classification per the Eyck et al, Rainbow Scale for Assessing Breast Ptosis at baseline and at day 180 post-treatment.
- 4. The Principal Investigator will complete a PGAIS assessing overall aesthetic improvement in the treatment area at day 30, 90, and 180 post-treatment.
- The subject will complete a SGAIS assessing overall aesthetic improvement in the treatment area at day 30, 90, and 180 post-treatment.
- 6. The subject will complete a Patient Satisfaction Questionnaire (PSQ) at the 180-day follow-up visit.
- 7. The subject will complete a Beast-Q survey at baseline and 180-day follow-up visit.

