#### 4.3.3.1.1 INDEPENDENT PHOTOGRAPHIC ASSESSMENTS

Three experienced, blinded photographic reviewers will perform a qualitative analysis/review of the pretreatment and post-treatment sets of images of each subject in a blinded and randomized order. Each blinded reviewer will choose which image is the post-treatment image. Success will be correct posttreatment image selection by at least 2 out of 3 reviewers. The percentage of subjects with a correct posttreatment image selection will be calculated.

Assessment of each subject's baseline and follow-up images viewed simultaneously will be performed by the Independent Photographic Reviewers (IPR) who will be blinded to the study subject's visit (baseline and follow-up visit). Each IPR will view each subject's randomized pre-treatment and post-treatment images and assess which set of images represent the subject's post-treatment images. Each photograph will have a unique identification number, but the sets of images will not be arranged in any specific order (i.e., randomized order).

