#### 4.3.3.1.2 INDEPENDENT PHOTOGRAPHIC REVIEW EVALUATION PROCESS

Each blinded assessor will be provided with identical photos to be assessed. The pre-treatment and posttreatment photos will be consistent in lighting, subject positioning, and focus. Each photo's visit interval, i.e., pre-treatment and post-treatment, will NOT be marked. The images placement (right or left) will be randomly ordered for pre-treatment and post-treatment images. Images for each subject will be grouped together into one set with all pre-treatment and post-treatment images in the same location (right/left) for the subject set.

Each blinded assessor will conduct their assessment independently with no input from another blinded assessor.

Each blinded assessor compares the Left and Right photo for change that may be striking (substantial and immediately noticeable), readily apparent but modest in nature, or slight and subtle in nature that may require close examination. Assessors should look through each view and assess change. Enough time should be allowed to do this for each subject, so the assessments are not rushed.

The assessor chooses which photo they believe to be the post-treatment photo (i.e., Left photo or Right photo) once all images in the subject set have been reviewed.

Post-Analysis Coding of Masked Assessment:

- If the assessor incorrectly chooses the post-treatment photo, this will be coded as an "Incorrect post-treatment selection".
- If the assessor correctly chooses the post-treatment photo, this will be coded as a "Correct post-treatment selection".

Λργχ *	
MEDICAL Apyx Medical Corporation	
Protocol Number: APX-22-03	Effective Date: 23SEP2022
	Revision No: 2.0
Title: Minimally Invasive Breast Lift Procedure Utilizing the Renuvion APR System	

• Success will be determined by correct identification of post-treatment photographs by at least two out of three blinded, independent reviewers.

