## 10. STATISTICAL METHODOLOGY

#### 10.1 STATISTICAL AND ANALYTICAL PLANS

For the purposes of this study, descriptive statistics will be performed.

MEDICAL Appx Medical Corporation	
Protocol Number: APX-22-03	Effective Date: 23SEP2022 Revision No: 2.0
Title: Minimally Invasive Breast Lift Procedure Utilizing the Renuvion APR System	

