#### 10.2 SAMPLE SIZE

The study will include up to 15 treated subjects from a single EU site.

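### Pure guessing scores 50% on the photographic 'Success' rate, yet the plan reports a bare percentage in at most 15 subjects, without that reference level, an interval or a defined denominator

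*Combined protocol and SAP*

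**What the plan says.** The photographic review is the first outcome listed in Section 4.3.1: "Independent Photographic Review of before and after images compared to baseline at D90 and baseline compared to D180". Section 4.3.3.1.2 has each assessor name either the left or the right image set as the post-treatment one, and specifies that "The images placement (right or left) will be randomly ordered for pre-treatment and post-treatment images". The subject-level rule is "Success will be determined by correct identification of post-treatment photographs by at least two out of three blinded, independent reviewers". Only correct or incorrect selection is coded, although assessors are told to consider changes ranging from striking to "slight and subtle in nature that may require close examination".

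For the summary, Section 4.3.3.1.1 says "The percentage of subjects with a correct posttreatment image selection will be calculated". The analysis plan in Section 10.1 adds only "For the purposes of this study, descriptive statistics will be performed", and Section 10.2 adds "The study will include up to 15 treated subjects from a single EU site". No section gives a guessing rate, a reference value or an interval.

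Three other places bear on the denominator. Section 5.5.2 does not replace withdrawals. Section 7.3.3 allows virtual visits at which photographs may be missing and records this as a deviation. The abbreviation list contains FAS, ITT, PP and PPS, but no analysis set is defined in the text.

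**The concern.** A forced choice between two images has a built-in score when there is nothing to see. Requiring two of three reviewers to be right looks stricter than relying on one, so a reader may assume that guessing scores well below 50%. It does not.

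The protocol labels the result 'Success', and in at most 15 subjects chance alone can move the percentage well above 50%. A figure of 60% or 67% may then be taken as evidence that the procedure works. Without the 50% level and an interval the reader cannot judge that, and without a defined n the same count can be shown as different percentages.

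The content of the measure matters too. The code carries neither size nor direction. A barely visible change, or a visible worsening that gives away the post-treatment set, counts the same as a marked lift.

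**Working it through.** **Inputs.** Three reviewers, a forced left/right choice, random placement and the two-of-three rule (Sections 4.3.3.1.1 and 4.3.3.1.2); at most 15 treated subjects (Section 10.2). The documents give no reference rate or confidence level and no derivation of 15, so there is no stated figure to reproduce. Assumed here: placement is 1:1 and independent between subjects, nothing in the images reveals their order, intervals are two-sided 95%, and 12 to 15 subjects are evaluable.

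**Step 1: guessing rate per subject.** With three independent guesses at 0.5,

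P(at least 2 of 3 correct) = 3 × 0.5² × 0.5 + 0.5³ = 0.375 + 0.125 = 0.500.

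Independence of the reviewers is not needed. Three reads always produce a majority side. If the sets look alike, the post-treatment set is on that side with probability 0.5, however much reviewers agree or favour one side. A simulation of 400,000 subjects, with each reviewer picking left 80% of the time and sharing a common pick 70% of the time, gave 0.500.

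**Step 2: what guessing produces in 15 subjects.** The count X is Binomial(15, 0.5), with expected value 15 × 0.5 = 7.5. The upper tail is the sum of C(15, k)/2¹⁵ from k = x to 15. For example, P(X ≥ 9) = 9949/32768 = 0.304 and P(X ≥ 10) = 4944/32768 = 0.151. The Clopper-Pearson limits are the 0.025 quantile of Beta(x, n − x + 1) and the 0.975 quantile of Beta(x + 1, n − x).

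| Successes / 15 | Percentage | Chance of this or more by guessing | Exact 95% CI | Width (points) |
|---|---|---|---|---|
| 8 | 53.3% | 0.500 | 26.6–78.7% | 52.1 |
| 9 | 60.0% | 0.304 | 32.3–83.7% | 51.4 |
| 10 | 66.7% | 0.151 | 38.4–88.2% | 49.8 |
| 11 | 73.3% | 0.059 | 44.9–92.2% | 47.3 |
| 12 | 80.0% | 0.018 | 51.9–95.7% | 43.8 |

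**Step 3: fewer evaluable subjects.**

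- n = 14: 10/14 (71.4%) or more has probability 0.090, CI 41.9–91.6%; 11/14 (78.6%) or more has probability 0.029, CI 49.2–95.3%.
- n = 13: 9/13 (69.2%) or more has probability 0.133; 10/13 (76.9%) or more has probability 0.046, CI 46.2–95.0%.
- n = 12: 8/12 (66.7%) or more has probability 0.194; 9/12 (75.0%) or more has probability 0.073.

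The exact interval lies above 50% only when the upper tail at 0.5 is below 0.025. The smallest such counts are 12/15 (0.018), 12/14 (106/16384 = 0.006), 11/13 (0.011) and 10/12 (0.019).

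**Step 4: denominator.** Suppose, for illustration, that 2 of 15 treated subjects have no usable photographs and 10 are successes. The rate is 10/13 = 76.9% or 10/15 = 66.7%, depending on a choice that the plan leaves open.

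**The case against.** The strongest reply is that this is a small, single-arm, post-market study with descriptive statistics only. No hypothesis, performance goal or decision hangs on the percentage. 'Success' is a coding rule for one subject, not a study-level claim, and the two-way choice is described openly, so a careful reader can work out the 50% level. An interval beside 50% may be used as an informal test, and the 95% level and the Clopper-Pearson method are not the plan's. Size and direction are covered by the morphometric measurements (4.3.3.8), the ptosis grade (4.3.3.7) and the GAIS (4.3.3.2), and reviewer training draws attention to lift (4.3.3.1.3).

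Part of this stands. It is a reporting gap, not a design flaw, and no test is called for. The summary does refer to subjects, so the denominator gap is an undefined analysis set and missing-image rule; that is a minor addition which would not carry the point alone. The 50% level is also conditional: any other cue to the order of the images, such as a visible incision mark, could raise the rate without any lift.

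The rest does not remove the point. A descriptive percentage still needs its reference level and precision to be read correctly. It is not obvious that a two-of-three rule leaves guessing at 50%, or that the interval at n = 15 is about 50 points wide. The other outcomes and the training do not change what a left/right code records.

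**Conclusion.** The concern holds. As planned, the first-listed outcome will be an uncalibrated percentage. A treatment with no visible effect is expected to score 50%, and in 15 subjects it would reach 60% or more about 3 times in 10 and 67% or more about 3 times in 20.

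The force is greatest for results of 60% to 67%. At 11/14 or 10/13 the conclusion depends on the interval method and on n: the one-sided tail is below 0.05, but the exact two-sided interval still includes 50%. At 12/15 and above the interval excludes 50%, and adding it would not weaken the result.

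This rests on 1:1 placement, independent between subjects, and on images that give no clue to their order other than a treatment effect. The plan should be changed, and before the results are known.

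**What to change.** Amend Sections 4.3.3.1.1 and 10.1 as follows.

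- **Summary.** Report the photographic review separately for D90 and D180 as x/n with the exact (Clopper-Pearson) 95% interval, beside the 50% guessing level.
- **Denominator.** Take n as treated subjects with baseline and follow-up image sets whose two-of-three result can be determined. Two agreeing reads are enough, because the third cannot change the outcome. Give the number treated and the reasons for exclusion at each time point.
- **Interpretation.** State that the measure shows whether a change can be detected, not by itself lift; that an interval above 50% does not say what made the sets distinguishable; and that an interval including 50% does not show absence of change.

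Keep this descriptive; no pass/fail threshold is needed. The cost is wording in two sections and one extra column in the results table, with no new data, reads or visits. For a given n the percentage itself does not change. The drawback for the sponsor is that it will look less favourable: with 15 subjects and 8 to 12 successes the interval is about 44 to 52 percentage points wide.

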#### 4.3.3.1.2 INDEPENDENT PHOTOGRAPHIC REVIEW EVALUATION PROCESS

Each blinded assessor will be provided with identical photos to be assessed. The pre-treatment and posttreatment photos will be consistent in lighting, subject positioning, and focus. Each photo's visit interval, i.e., pre-treatment and post-treatment, will NOT be marked. The images placement (right or left) will be randomly ordered for pre-treatment and post-treatment images. Images for each subject will be grouped together into one set with all pre-treatment and post-treatment images in the same location (right/left) for the subject set.

Each blinded assessor will conduct their assessment independently with no input from another blinded assessor.

Each blinded assessor compares the Left and Right photo for change that may be striking (substantial and immediately noticeable), readily apparent but modest in nature, or slight and subtle in nature that may require close examination. Assessors should look through each view and assess change. Enough time should be allowed to do this for each subject, so the assessments are not rushed.

The assessor chooses which photo they believe to be the post-treatment photo (i.e., Left photo or Right photo) once all images in the subject set have been reviewed.

Post-Analysis Coding of Masked Assessment:

- If the assessor incorrectly chooses the post-treatment photo, this will be coded as an "Incorrect post-treatment selection".
- If the assessor correctly chooses the post-treatment photo, this will be coded as a "Correct post-treatment selection".

Λργχ *	
MEDICAL Apyx Medical Corporation	
Protocol Number: APX-22-03	Effective Date: 23SEP2022
	Revision No: 2.0
Title: Minimally Invasive Breast Lift Procedure Utilizing the Renuvion APR System	

• Success will be determined by correct identification of post-treatment photographs by at least two out of three blinded, independent reviewers.

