#### 2.2 POTENTIAL RISKS AND BENEFITS

#### 2.2.1 POTENTIAL RISKS

This treatment modality was designed to inherently minimize the risk to the subject. However, treatment with energy-based modalities (laser, radiofrequency, and plasma devices) produce subsequent heating of the soft tissue that could involve the following commonly Expected Treatment Effects (ETEs): discomfort/pain, edema, erythema, ecchymosis, hypoesthesia, temporary sensory nerve injury (touch sensitivity, itching, temporary numbness/tingling), transient migratory firmness, and temporary and/or transient crepitus.

In addition to commonly expected treatment effects, treatment with the Renuvion APR device could involve the following risks: helium embolism into the surgical site due to inadvertent introduction into the venous or arterial blood supply system, unintended burns (deep or superficial), pneumothorax, temporary or permanent motor nerve injury, ischemia, fibrosis, infection, gas buildup, bleeding, hematoma, seroma, subcutaneous induration, pigmentation changes, increased healing time, unsatisfactory scarring, asymmetry and/or unacceptable cosmetic result.

Risks associated with tumescent anesthesia (lidocaine and epinephrine) include blurred vision, mental/mood changes, drowsiness, dizziness, unusually slow heartbeat, rash, itching, swelling, anxiety, apprehensiveness, restlessness, tremor, weakness, sweating, palpitations, pallor, nausea and vomiting, headache, and respiratory difficulties.

Subjects using drugs that reduce coagulation (aspirin or NSAIDs) may experience increased bruising or bleeding at the treatment site. Any other medication prescribed for the procedure or after-procedure by the investigator have their own risks; these risks should be discussed with the subject.

A grounding pad is used to ground/neutralize the electrical current. Subjects undergoing radiofrequency treatment will be kept away from contact with metal parts which are grounded, or which have appreciable capacitance to earth.

Any unexpected or unforeseen complications will be managed by the investigator throughout the conduct of the study. Unforeseen or unexpected side effects not listed above will be reported to the sponsor and regulatory representatives (Ethics Committee) as they occur.

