#### 4.3.3.1.3 INDEPENDENT PHOTOGRAPHIC REVIEW TRAINING PROCESS

IPR assessors will participate in a training session prior to completing the IPR. The purpose of the training is to provide guidance to the IPR assessors on the methods for reviewing the study images and to provide sample images for scoring and discussion of the scoring by IPR assessors. Instructions will include that each blinded assessor should pay close attention to changes in overall appearance of lift in the treatment area.

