#### 7.2 STUDY PROCEDURE

On the day of the procedure and prior to the study procedure, female subjects with child-bearing potential must complete a urine pregnancy test (result must be obtained prior to the procedure).

All study subjects will be treated with the Renuvion APR Device. The treatment area is defined as superior most not to exceed a horizontal line from the superior aspect of the axilla to the midline; inferior most not to cross the junction of the breast with the abdomen (inframammary fold). Lateral border to the outermost curvature of the breast or a vertical line drawn from the preaxillary line to the IMF; medial most to the innermost curvature of the breast of to 1 cm lateral to the sternal midline. The procedure will be in the intradermal and subdermal planes in the upper breast area, without penetrating the breast gland.

After undermining, the Renuvion APR device treatment will be performed using up to 6 retrograde or 3 antegrade/retrograde treatment passes with settings of 60- 70% power and 1.5 LPM of helium flow with an activation speed of approximately 1-3 cm/s. A minimum of 2 incision sites will be used for the treatment that are well-hidden in the areola border (approximately 3 and 9 o'clock positions) and pre-axillary fold or in the inframammary fold on the lateral and medial sides of each breast. The study procedure will be in the intradermal and subdermal planes in the upper breast area, without penetrating the breast gland while using a crosshatching pattern.

During the procedure, fat transfer and any other procedure outside of the study specified procedure is not allowed.

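### Photo-review success is scored on picking out the post-treatment set, with no direction of change recorded, so a correct pick prompted by a scar, asymmetry or worsening counts the same as one prompted by lift

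*Combined protocol and SAP*

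**What the plan says.** Section 4.3.1 lists the independent photographic review first among seven outcome measures, comparing baseline with Day 90 and baseline with Day 180. Section 4.3.3.1.1 sets the rule for a subject: "Success will be correct posttreatment image selection by at least 2 out of 3 reviewers". The percentage of subjects meeting it is the reported statistic. Section 4.3.3.1.2 repeats the rule: "Success will be determined by correct identification of post-treatment photographs by at least two out of three blinded, independent reviewers".

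The same section describes the reviewer's task. "Each blinded assessor compares the Left and Right photo for change that may be striking", or modest, or subtle; these words grade the size of a change, not its direction. Then "The assessor chooses which photo they believe to be the post-treatment photo". Two codes are specified, a correct and an incorrect selection.

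Direction comes in only through training. Section 4.3.3.1.3 tells reviewers to "pay close attention to changes in overall appearance of lift in the treatment area". That instruction is not carried into the coding or the success rule.

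Two other sections bear on what reviewers might see. Section 2.2.1 lists among the device risks "pigmentation changes, increased healing time, unsatisfactory scarring, asymmetry and/or unacceptable cosmetic result". Section 7.2 calls for at least two incision sites. The first placement it offers is described as "well-hidden in the areola border (approximately 3 and 9 o'clock positions"), together with a site near the armpit. The second placement, given as an alternative to the first, reads "or in the inframammary fold on the lateral and medial sides of each breast".

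**The concern.** The study evaluates a breast lift, so a reader will take a blinded success percentage as evidence of lift. The rule does not ask about lift. A reviewer who sees none must still choose a side and may use any visible difference: a mark at the areola, a change in pigment, an asymmetry, or a breast that looks worse. If the choice is right, it is a success.

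This matters more because the photographic review is the only outcome whose assessment is described as blinded. The Global Aesthetic Improvement Scale (GAIS), the ptosis grade and the morphometric measurements do record direction, but their sections describe no blinding and they do not feed into photo-review success. GAIS is rated by the subject and by the investigator or a delegate, against known pre-treatment photographs. Because the protocol specifies no record of direction or reason, the share of the percentage that reflects lift could not be worked out afterwards.

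**Working it through.** **No planned figure to reproduce.** Section 10.1 plans descriptive statistics only, and Section 10.2 gives up to 15 treated subjects. There is no target rate, threshold, test or power calculation.

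**Inputs from the protocol.** Three reviewers, a two-way choice, success at two or more correct (Sections 4.3.3.1.1 and 4.3.3.1.2), and 15 subjects.

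**Formula.** If each reviewer independently picks correctly with probability p, a subject is a success with probability

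S(p) = 3p²(1 − p) + p³.

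**Step 1: pure guessing.** S(0.5) = 3 × 0.25 × 0.5 + 0.125 = 0.500, and 15 × 0.500 = 7.5 subjects expected. This follows from the rule alone.

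**Step 2: no lift, but a non-lift cue.** Assume each reviewer notices the cue with probability q, then picks correctly, and otherwise guesses. Then p = q + (1 − q)/2. The documents give no value for q, so a range is shown. The last two columns replace independent noticing with a cue seen by all three reviewers or by none, which gives q + (1 − q) × 0.5.

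| q (assumed) | p | S(p), independent | Expected of 15 | Shared cue | Expected of 15 |
|---|---|---|---|---|---|
| 0.1 | 0.55 | 0.57475 (57%) | 8.6 | 55% | 8.25 |
| 0.3 | 0.65 | 0.71825 (72%) | 10.8 | 65% | 9.75 |
| 0.5 | 0.75 | 0.84375 (84%) | 12.7 | 75% | 11.25 |

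**Step 3: lift and cue cannot be separated.** Suppose instead that there is no cue, and that lift is present and is what reviewers notice, with the same probability q. The formula for p is unchanged, so 84% arises at q = 0.5 either way. Nothing the protocol says will be recorded distinguishes the two.

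**Step 4: a subject who has worsened.** Let h be the assumed probability that a reviewer takes the worse-looking set as post-treatment. Success is S(h):

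- h = 0.25: 3 × 0.0625 × 0.75 + 0.015625 = 0.156 (16%)
- h = 0.50: 0.500 (50%)
- h = 0.75: 3 × 0.5625 × 0.25 + 0.421875 = 0.844 (84%)

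Worsening is therefore scored as success or failure according to how reviewers reason, which the plan does not control.

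**The case against.** Several points on the other side are fair.

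- **Training and worsening.** A reviewer trained on lift who expects improvement will tend to call the better-looking set post-treatment, so some worsening will be coded incorrect. This stands. Worsening has no definite net direction, and only non-lift cues push the percentage up. A correct pick prompted by worsening still counts as success.
- **Visibility of cues.** The incisions are described as well hidden, the inframammary fold is an alternative site, and the comparisons are at three and six months. This stands as a limit on size: how often a cue would be visible cannot be learned from the documents.
- **Shared detection.** A scar or asymmetry belongs to the subject, so reviewers may all see it or all miss it. The shared-cue columns allow for this; the rates are lower but still at or above 55%.
- **Descriptive study, accurate label.** The statistic is named as the percentage correctly selected, and no decision rule depends on it. This limits the consequence to interpretation. But the protocol itself calls a correct pick success, in a study of lift.
- **Direction is measured elsewhere.** GAIS, ptosis grade, morphometric distances and the satisfaction questionnaire all carry direction. The synopsis calls the study evaluator-blinded, and Section 4.3.3.7 does not name the Day 180 ptosis rater, so the absence of blinding there is silence, not a stated fact. None of these outcomes conditions the photographic result.
- **Unseen reviewer form.** The form is not in the documents and might collect more. Even so, the coding and the success rule that are stated use only the identification answer.

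**Conclusion.** The concern holds. As written, the outcome measures detectability of the procedure in photographs, and its success percentage cannot show how much is due to lift. That conclusion follows from the coding rule and needs no assumption. The 50% chance level also follows from the rule, given independent guessing, and the protocol does not mention it.

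The size of any inflation does rest on assumption. With zero lift, the illustrated success rate runs from 55% to 84% for q between 0.1 and 0.5, depending also on whether reviewers notice cues independently or together. The effect of worsening could go either way. No formal test is at risk, because none is planned. What is at risk is the meaning of the one result whose assessment is described as blinded, so the rule should be corrected before the photographic review is run.

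**What to change.** In Sections 4.3.3.1.1 and 4.3.3.1.2:

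1. Ask first: *Which set shows the more lifted breasts, Left or Right?*
2. Define success as two or more of the three reviewers choosing the post-treatment set as the more lifted.
3. Report the percentage at Day 90 and at Day 180 beside the 50% chance level.
4. Once the lift answer is locked, ask which set is post-treatment. Report this as a descriptive item and do not call it success.
5. State as a remaining limitation that visible marks can still influence the lift answer through expectation.

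This brings the scoring into line with the training instruction in Section 4.3.3.1.3. The cost is a reworded reviewer form, coding rule and training material, with one added question, and a protocol amendment approved by the ethics committee under Section 15.2. Reviewers, images and chance level are unchanged. The drawbacks are that the success figure may be lower, and that the change reduces but does not remove the influence of visible marks.
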